6 STUDY POPULATION

6.1 Study Entry Criteria

6.1.1 Inclusion Criteria

Patients must meet all of the applicable criteria to be eligible for enrollment in this study:

1. Willing and able to sign the approved informed consent.
2. Age: 18+ years old at Screening.
3. Diagnosis (a., b., and c. required) of **EITHER** *Acute Myeloid Leukaemia*:
 - a. By World Health Organization (WHO) criteria regardless of etiology, sub-type or treatment history.
 - b. High risk AML* diagnosis in accordance with one of the following classifications:
 - ≥ 60 years of age with AML who are **not** candidates for (based on parameters such as performance scores, co-morbidities and cytogenetic studies), or have refused, standard chemotherapy
 - 18+ year old with *de novo* or secondary AML (MDS/AML or treatment-related (t)-AML) who are **not** expected to benefit from standard remission-induction chemotherapy (unfavorable cytogenetics)
 - Relapsed/refractory AML after no more than 3 previous lines of chemotherapy, including hypomethylating agents, for whom no standard therapies are available
 - c. Eastern Cooperative Oncology Group (ECOG) performance status score ≤2.

*All forms of AML (M0–M7) diagnosed by morphologic, histochemical or cell surface marker criteria.

OR *Myelodysplastic Syndromes*:

- a. By WHO criteria regardless of sub-type.
 - b. High Risk MDS diagnosis in accordance with one of the following classifications:
 - MDS patients who have failed first-line therapy, demonstrated by resistance to, or relapse following a minimum of 4 cycles with a hypomethylating agent (HMA)
 - Treatment-related MDS, except if it is associated with favorable cytogenetics, and **not** a candidate for stem cell transplantation
 - c. Either an International Prognostic Scoring System (IPSS) score equivalent to intermediate-2 risk or higher, or a Revised International Prognostic Scoring System (IPSS-R) score equivalent to intermediate risk or higher.
4. Prior autologous stem cell transplant is allowed if a minimum of 3 months has elapsed from the time of transplant and the patient has recovered from transplant-associated toxicities.
 5. Prior allogeneic stem cell transplant is allowed, provided all of the following criteria are met:
 - a. Transplant was >120 days prior to study enrollment
 - b. No immunosuppressive medications have been taken for at least 1 month
 - c. No active graft versus host disease (GVHD), excluding Grade 1 skin GVHD

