2	Ambulatory and capable of all self-care but unable to carry out any work activities; up and about more than 50% of waking hours
3	Capable of only limited self-care; confined to bed or chair more than 50% of waking hours
4	Completely disabled; cannot carry on any self-care; totally confined to bed or chair
5	Dead

Table 11: 2016 WHO Classification System for Myelodysplastic Syndromes (Arber *et al.*, 2016)

Disease	Dysplastic lineages	Cytopenias*	Ring sideroblasts as % of marrow erythroid elements	Blood Findings	Bone Marrow Findings	Cytogenetics by conventional karyotype analysis
MDS with single lineage dysplasia (MDS-SLD)	1	1 or 2	<15%/<5%†	<1% blasts no Auer rods	<5% blasts no Auer rods	Any, unless fulfills all criteria for MDS with isolated del(5q)
MDS with multilineage dysplasia (MDS-MLD)	2 or 3	1-3	<15%/<5%†	<1% blasts no Auer rods	<5% blasts no Auer rods	Any, unless fulfills all criteria for MDS with isolated del(5q)
MDS with ring sideroblasts (MDS-RS)						
MDS-RS and single lineage dysplasia (MDS-RS-SLD)	1	1 or 2	≥15%/≥5%†	<1% blasts no Auer rods	<5% blasts no Auer rods	Any, unless fulfills all criteria for MDS with isolated del(5q)
MDS-RS and multilineage dysplasia (MDS-RS-MLD)	2 or 3	1-3	≥15%/≥5%†	<1% blasts no Auer rods	<5% blasts no Auer rods	Any, unless fulfills all criteria for MDS with isolated del(5q)
MDS with isolated del(5q)	1-3	1-2	None or any	<1% blasts no Auer rods	<5% blasts no Auer rods	del(5q) alone or with 1 additional abnormality except -7 or del(7q)
MDS with excess blasts (MDS-EB)						
MDS with excess blasts-1 (MDS-EB-1)	0-3	1-3	None or any	2-4% blasts no Auer rods	5-9% blasts no Auer rods	Any
MDS with excess blasts-2 (MDS-EB-2)	0-3	1-3	None or any	5-19% blasts or Auer rods	10-19% blasts or Auer rods	Any
MDS, unclassified (MDS-U)						
With 1% blasts	1-3	1-3	None or any	=1% blasts‡ no Auer rods	<5% blasts no Auer rods	Any
With single lineage dysplasia and pancytopenia	1	3	None or any	<1% blasts no Auer rods	<5% blasts no Auer rods	Any
Based on defining cytogenetic abnormality	0	1-3	<15%§	<1% blasts no Auer rods	<5% blasts no Auer rods	MDS-defining abnormality
Provisional entity: Refractory cytopenia of childhood	1-3	1-3	None	<2% blasts	<5% blasts	Any

*Cytopenias defined as: haemoglobin, <10 g/dL; platelet count, <100 x 10⁹/L; and absolute neutrophil count, <1.8 x 10⁹/L. Rarely, MDS may present with mild anemia or thrombocytopenia above these levels. PB monocytes must be <1 x 10⁹/L

† If *SF3B1* mutation is present.

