‡One percent PB blasts must be recorded on at least 2 separate occasions.

§Cases with ≥15% ring sideroblasts by definition have significant erythroid dysplasia, and are classified as MDS-RS-SLD.

Table 12: International Prognostic Scoring System (IPSS) and Risk Categories for Myelodysplastic Syndrome

PROGNOSTIC CHARACTERISTICS	POINTS				
	0	0.5	1	1.5	2
Cytogenetic risk category ^a	Good	Intermediate	Poor		
Blasts in bone marrow	<5%	5-10%		11-20%	21-30%
Cytopenias ^b	0 or 1	2 or 3			

^aGood: normal, -Y, del(5q), or del(20q) as single abnormalities; Intermediate: abnormalities other than good or poor; Poor: complex, 3 or more abnormalities, abnormal chromosome 7.

^bEach of the following cytopenia counts as a value of 1: haemoglobin < 10 g/dl; absolute neutrophil count (ANC) < 1,500×10⁹/L; platelet count less than 100,000×10⁹/L

IPSS Risk Category	Score
Low	0
Intermediate-1	0.5-1.0
Intermediate-2	1.5-2.0
High	> 2.0

Table 13: Revised International Prognostic Scoring System (IPSS-R) and Risk Categories for Myelodysplastic Syndromes

PROGNOSTIC CHARACTERISTICS	POINTS						
	0	0.5	1	1.5	2	3	4
Cytogenetic risk category ^a	Very good		Good		Intermediate	Poor	Very poor
Blasts in bone marrow, %	≤2		>2%–5%		5%–10%	>10%	
Haemoglobin, g/dl	≥10		8–<10	<8			
Platelet count, ×10 ⁹ /l	≥100	50–<100	<50				
Absolute neutrophil count, ×10 ⁹ /l	≥0.8	<0.8					

^aVery good: -Y and del(11q) as single abnormalities; good: normal, del(5q), del(12p) and del(20q) as single abnormalities, double abnormalities including del(5q); intermediate: del(7q), +8, +19, i(17q) and any other single abnormalities, any other double abnormalities; poor: -7 and inv(3)/t(3q)/del(3q) as single abnormalities, double abnormalities including -7/del(7q), complex (3 abnormalities); very poor: >3 abnormalities.

IPSS-R Risk Category	Score
Very low	≤1.5
Low	>1.5–3
Intermediate	>3–4.5
High	>4.5–6
Very high	> 6

Table 14 Response criteria in AML

Category	Definition
Complete remission (CR)*	Bone marrow blasts < 5%; absence of blasts with Auer rods; absence of extramedullary disease; absolute neutrophil count > 1.0 x 10 ⁹ /L (1000/μL); platelet count > 100 x 10 ⁹ /L (100 000/μL); independence of red cell transfusions
CR with incomplete recovery (CRi)	All CR criteria except for residual neutropenia (< 1.0 x 10 ⁹ /L [1000/μL]) or thrombocytopenia (< 100 x 10 ⁹ /L [100 000/μL])

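### Protocol Table 12 prints the IPSS neutrophil and platelet cut-offs 1000-fold too high; read literally, MDS patients with 0 or 1 true cytopenia gain 0.5 points, and a narrow group would cross the IPSS entry line

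*Protocol*

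**What the plan says.** Table 12 in Protocol Section 16.2 is the only IPSS scoring table in either document. Its footnote b counts one cytopenia for haemoglobin below 10 g/dl and one each for "absolute neutrophil count (ANC) < 1,500×10⁹/L; platelet count less than 100,000×10⁹/L". The table gives 0 points for none or one cytopenia and 0.5 points for two or three. The category table beneath it starts the second intermediate band at 1.5: "Intermediate-2 1.5-2.0".

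For MDS, inclusion criterion 3c (Section 6.1.1) can be met in either of two ways:

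- IPSS: "Either an International Prognostic Scoring System (IPSS) score equivalent to intermediate-2 risk or higher"
- IPSS-R: "Revised International Prognostic Scoring System (IPSS-R) score equivalent to intermediate risk or higher"

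Criteria 3a and 3b must be met as well. Footnote a to Section 16.1.1 has sites document the IPSS or IPSS-R score at Screening. The SAP (Section VII.A, MDS baseline disease history) lists and summarises IPSS risk.

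Other tables in Section 16.2 use the ordinary scale. The Table 11 footnote gives "platelet count, <100 x 10⁹/L; and absolute neutrophil count, <1.8 x 10⁹/L". Table 14 pairs the two units directly: "absolute neutrophil count > 1.0 x 10 ⁹ /L (1000/μL".

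**The concern.** A cut-off that no patient can exceed does not discriminate. If Table 12 is applied as printed, the zero-point cytopenia cell can never be used and every error runs the same way, toward higher risk. Two uses are exposed. One is the IPSS route through criterion 3c, where half a point separates Intermediate-1 (top score 1.0) from Intermediate-2 (from 1.5). The other is the IPSS distribution that the SAP reports as a baseline characteristic. The study treats about 40 AML and MDS patients in all, in cohorts that may hold as few as three, so even one reclassified patient would be visible in a by-cohort table.

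**Working it through.** **Step 1: units.** Table 14 equates 1.0×10⁹/L with 1000/µL and 100×10⁹/L with 100 000/µL. Criteria 6 and 7 equate 30×10⁹/L with 30,000/µL. Hence 1,500/µL = 1.5×10⁹/L and 100,000/µL = 100×10⁹/L. The printed figures exceed these by 1,500/1.5 = 1000 and 100,000/100 = 1000. The platelet value of 100×10⁹/L appears in Tables 11, 13, 14 and 15. An ANC value of 1.5×10⁹/L appears nowhere else; it follows from reading 1,500 as per µL.

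**Step 2: literal reading.** Criterion 6 caps WBC at 30×10⁹/L, so ANC is at most 30×10⁹/L, below 1,500×10⁹/L. A platelet count of 100,000×10⁹/L is not physiologically possible. Both cytopenias are therefore always counted, and the cytopenia item always scores 0.5.

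**Step 3: effect on the score.** Patients with 2-3 true cytopenias already score 0.5 and do not change. For 0-1 true cytopenia, the score is cytogenetic points + blast points + 0 with the rescaled cut-offs, and + 0.5 as printed. Each cell shows rescaled → printed; bold marks a change of category.

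| Cytogenetics (points) | Blasts <5% (0) | 5-10% (0.5) | 11-20% (1.5) | 21-30% (2) |
|---|---|---|---|---|
| Good (0) | **0 Low → 0.5 Int-1** | 0.5 → 1.0, Int-1 | 1.5 → 2.0, Int-2 | **2.0 Int-2 → 2.5 High** |
| Intermediate (0.5) | 0.5 → 1.0, Int-1 | **1.0 Int-1 → 1.5 Int-2** | **2.0 Int-2 → 2.5 High** | 2.5 → 3.0, High |
| Poor (1) | **1.0 Int-1 → 1.5 Int-2** | 1.5 → 2.0, Int-2 | 2.5 → 3.0, High | 3.0 → 3.5, High |

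Five of 12 combinations change category. Two of those cross the 1.5 line used in criterion 3c.

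**Step 4: the IPSS-R route.** IPSS-R intermediate starts above 3 (Table 13). Three patients from the two crossing cells, each with normal ANC and platelets:

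| Patient | IPSS rescaled | IPSS printed | IPSS-R | Does Table 12 decide 3c? |
|---|---|---|---|---|
| +8, blasts above 5% up to 10%, Hb ≥10 | 0.5+0.5+0 = 1.0 | 1.5 | 2+2 = 4.0, Intermediate | No, already admitted |
| Isolated del(12p), blasts above 5% up to 10%, Hb ≥10 | 0.5+0.5+0 = 1.0 | 1.5 | 1+2 = 3.0, Low | Yes |
| Isolated del(7q), blasts ≤2%, Hb 9 | 1+0+0 = 1.0 | 1.5 | 2+0+1 = 3.0, Low | Yes |

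To see how wide this gap is, take a grid of Hb 7.5, 9, 11 g/dl; ANC 0.5, 1.2, 2.5×10⁹/L; and platelets 40, 75, 150×10⁹/L. Seven profiles have 0-1 true cytopenia. The number of those seven that IPSS-R also leaves out is:

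| Crossing cell | IPSS-R karyotype group and blasts | Below IPSS-R intermediate |
|---|---|---|
| IPSS intermediate, 5-10% blasts | Very good, e.g. del(11q) | 6 of 7 |
| | Good, e.g. del(12p) | 2 of 7 |
| | Intermediate, e.g. +8 | 0 of 7 |
| IPSS poor, <5% blasts | del(7q) alone, ≤2% | 6 of 7 |
| | del(7q) alone, >2% to <5% | 2 of 7 |
| | -7 or three abnormalities, ≤2% | 2 of 7 |
| | -7 or three abnormalities, >2% to <5% | 0 of 7 |
| | More than three abnormalities, any <5% | 0 of 7 |

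These count grid points, not patients. They show only that IPSS-R closes part of the gap.

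**The case against.** The strongest reply is that this is a recognisable misprint with little reach. A haematologist would not score every patient as thrombocytopenic, and the protocol supplies the correct conversion in several places. Criterion 3c names the IPSS without citing Table 12, whereas the treatment-failure text (Section 6.8) cites Tables 14 and 15 by number. The SAP does not specify a derivation of IPSS risk from Table 12. The summary is descriptive, and SAP Section VI.F rules out covariate adjustment. All of this stands, and it limits the likely effect. It does not make the printed threshold right, and neither document offers another IPSS definition.

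A reader might infer that lower-risk MDS patients can enter by arithmetic alone. The documents do not support that. Criterion 3b separately requires hypomethylating-agent failure, or treatment-related MDS without favourable cytogenetics in a patient who is not a transplant candidate. The IPSS-R alternative in 3c already admits patients such as the +8 case, whatever Table 12 says.

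A reader might also infer that IPSS must be re-derived for every enrolled MDS patient. That is not shown to be feasible. Section 10.1.1 brings cytogenetics into the eCRF only where a local result is available, and Section 10.1.2 makes central FISH optional. Nor do the documents show that any site used the misprinted values.

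**Conclusion.** The concern holds in limited form. Both cut-offs in footnote b carry a 1000-fold unit error, provable from the protocol's own conversions. Applied literally, the error adds 0.5 points for every MDS patient with 0-1 true cytopenia, changes category in 5 of 12 cytogenetic-by-blast combinations, and crosses the IPSS entry line in 2 of them. Eligibility changes only where three conditions meet: a correct IPSS of 1.0 with 0-1 true cytopenia, criterion 3b satisfied, and IPSS-R of 3 or less.

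The number of patients affected cannot be worked out, because the documents give neither the MDS share of the roughly 40 patients nor the method sites used to score. The practical effect is probably small. The conclusion assumes that 1,500 was meant per µL, and every stated consequence assumes that the table is applied as printed.

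**What to change.** Correct the units in Table 12 footnote b to 1,500/µL and 100,000/µL (1.5 and 100×10⁹/L), in line with the rest of Section 16.2. This is a one-line change.

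Before the SAP baseline table is run, check the site-recorded IPSS category against baseline counts for MDS patients who entered 3c on IPSS alone or whose cytogenetics are recorded. Haemoglobin, ANC and platelets are enough for a first pass: a patient with two or three true cytopenias has the same score either way and needs no further work. For those with 0-1, use recorded cytogenetics and blasts, or ask the site how the cytopenia item was scored. Where the category cannot be verified, report it as recorded and say so. The cost is a short programmed check on haematology already collected and perhaps a few site queries.

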Patients who either fail to demonstrate stable disease, demonstrate progressive disease after achieving partial remission (PR) or stable disease, or relapse after achieving complete remission (CR), CR with incomplete recovery (CRi), or PR (see **Table 14** and **Table 15**) are the equivalent of treatment failures, and will discontinue study drug and enter the follow-up period.

Patients will be followed closely for both Adverse Events (AEs) and signs of toxicity by frequent monitoring of clinical signs and symptoms and by blood and urine analyses both during the IMG-7289 treatment period and the rest period. Pharmacodynamic effects will also be closely monitored by frequent haematology assessments of peripheral blood and bone marrow aspirates, as required.

All patients will undergo End-of-Treatment (EOT), pre-End of Study (pre-EOS), and End-of-Study (EOS) visits approximately 7, 14, and 28 days, respectively, after last Cycle last dose.

A detailed description by-cohort, by-cycle, of assessments to be performed is provided in Section 9. Additionally, a by-cohort schema of assessments is included in Section 16.1, Schedule of Assessments.

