*All criteria need to be fulfilled; marrow evaluation should be based on a count of 200 nucleated cells in an aspirate with spicules; if ambiguous, consider repeat exam after 5 to 7 days; flow cytometric evaluation may help to distinguish between persistent leukaemia and regenerating normal marrow; a marrow biopsy should be performed in cases of dry tap, or if no spicules are obtained; no minimum duration of response required.
¶In cases with low blast percentages (5-10%), a repeat marrow should be performed to confirm relapse. Appearance of new dysplastic changes should be closely monitored for emerging relapse. In a patient who has been recently treated, dysplasia or a transient increase in blasts may reflect a chemotherapy effect and recovery of haematopoiesis. Cytogenetics should be tested to distinguish true relapse from therapy-related MDS/AML.

Table 15: Response Criteria for MDS

Category	Response Criteria (responses must last at least 4 weeks)
Complete remission	Bone marrow: ≤ 5% myeloblasts with normal maturation of all cell lines* Persistent dysplasia will be noted*† Peripheral blood‡ Hgb ≥ 11 g/dL Platelets ≥ 100 x 10 ⁹ /L Neutrophils ≥ 1.0 x 10 ⁹ /L† Blasts 0%
Partial remission	All CR criteria if abnormal before treatment except: Bone marrow blasts decreased by ≥ 50% over pretreatment but still > 5% Cellularity and morphology not relevant
Marrow CR†	Bone marrow: ≤ 5% myeloblasts and decrease by ≥ 50% over pretreatment† Peripheral blood: if HI responses, they will be noted in addition to marrow CR†
Stable disease	Failure to achieve at least PR, but no evidence of progression for > 8 wks
Failure	Death during treatment or disease progression characterized by worsening of cytopenias, increase in percentage of bone marrow blasts, or progression to a more advanced MDS FAB subtype than pretreatment
Relapse after CR or PR	At least 1 of the following: Return to pretreatment bone marrow blast percentage Decrement of ≥ 50% from maximum remission/response levels in granulocytes or platelets Reduction in Hgb concentration by ≥ 1.5 g/dL or transfusion dependence
Cytogenetic response	Complete: Disappearance of the chromosomal abnormality without appearance of new ones Partial: At least 50% reduction of the chromosomal abnormality

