The primary objective, the adequacy of IMG-7289 dose and duration with and without ATRA in producing a pharmacodynamic effect, will be determined using serial blood and bone marrow sampling throughout the course of treatment with responses documented according to revised/modified International Working Group (IWG) Response Criteria – [Cheson *et al.* 2003](#) for AML and [Cheson *et al.* 2006](#) for MDS as described in Protocol Section 16.2. Response is to be assessed each time a bone marrow aspirate or biopsy is performed, with the exception of baseline. All available response data will be listed. The visit overall response per patient, as determined by the Investigator, and recorded on the eCRF, will be listed and summarized for each cohort, using the Efficacy Population.

The best response of each AML patient will be programmatically selected based on the following order: Complete Remission (CR), CR w/Incomplete Recovery (CRi), Morphologic Leukaemia-Free State (MLFS), Partial Remission (PR), Cytogenetic CR (CRc), Molecular CR (CRm), Stable Disease (SD), Resistant Disease (RD), Relapse (Rel), Progressive Disease (PD), Death from Indeterminate Cause (DInd), Death in Aplasia (DiA), and Not Evaluable. The best response of each MDS patient will be programmatically selected based on the following order: Complete Remission (CR), Partial Remission (PR), Marrow CR (CRm), Cytogenetic Response (CyR), Stable Disease (SD), Relapse After CR or PR (Rel), Disease Progression (DP), Failure: Disease Progression (FDP), Survival (Sur), Failure: Death During Treatment (FDDT), and Not Evaluable.

Objective response in AML includes Complete remission (CR), CR with incomplete recovery (CRi), Morphologic leukemia-free state, Partial remission (PR), Cytogenetic CR (CRc), and Molecular CR (CRm) and Stable Disease (SD); while objective response in MDS includes Complete remission (CR), Partial remission (PR), Marrow CR, or Cytogenetic response (CyR) and Stable Disease (SD). Objective response rate (ORR) is the proportion of responders with AML or MDS. ORR and its Fisher exact 95% confidence interval will be presented.

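### The SAP selects the best MDS response visit by visit with no duration check, so a response lost within the protocol's 4-week minimum can stand as best response

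*Protocol*

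**What the plan says.** Protocol Section 16.2, Table 15 (MDS) puts a duration condition in its column heading: "Response Criteria (responses must last at least 4 weeks". A footnote adds that transient cytopenias during repeated courses do not break durability, provided counts recover. The footnote to Table 14 (AML) says the opposite about duration: "no minimum duration of response required".

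SAP Section VIII.A adopts these criteria by reference ("for MDS as described in Protocol Section 16.2") and then sets the mechanics:
- Timing: "Response is to be assessed each time a bone marrow aspirate or biopsy is performed, with the exception of baseline".
- Source: "The visit overall response per patient, as determined by the Investigator, and recorded on the eCRF, will be listed and summarized for each cohort".
- Selection: "The best response of each MDS patient will be programmatically selected based on the following order". The order starts with CR, PR, marrow CR, cytogenetic response and SD. Relapse and progression come below all of these.
- Rate: "while objective response in MDS includes Complete remission (CR), Partial remission (PR), Marrow CR, or Cytogenetic response (CyR) and Stable Disease (SD". ORR is the proportion of such patients, AML and MDS together, with an exact 95% interval.

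Follow-up is fixed by Protocol Section 5.1, with EOT, pre-EOS and EOS "visits approximately 7, 14, and 28 days, respectively, after last Cycle last dose". The schedule in Section 16.1.1 asks for marrow at EOT and EOS.

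**The concern.** The protocol makes durability part of the definition of an MDS response and leaves it out for AML. The SAP applies one algorithm to both. A call made at the first responding marrow cannot contain the next 4 weeks, and because relapse and progression rank below every response, a later loss never displaces the earlier call. SAP Section VIII.A contains no minimum interval, confirming assessment or unconfirmed category.

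At stake is the reported MDS best-response category. SAP Section VIII.A uses these responses to judge a primary objective, the adequacy of dose and duration. ORR is affected less directly, because SD also counts there.

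**Working it through.** There is no stated figure to reproduce. The check has three parts.

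**1. Can the scheduled marrows show 4 weeks?** Inputs are cycle lengths and initial cycle numbers (Protocol Tables 1, 2 and 4), marrow visits (Section 16.1) and follow-up timing (Section 5.1). Last dose = (cycles − 1) × cycle length + dosing days; EOT = last dose + 7; EOS = last dose + 28. For a patient who stops after the initial cycles, EOT replaces the last rest-day visit.

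| Cohort | Cycle length | Last dose | EOT | EOS | Post-baseline marrow days | Gaps |
|---|---|---|---|---|---|---|
| 1 | 7 + 7 = 14 | 3 × 14 + 7 = 49 | 56 | 77 | 28, 56, 77 | 28, 21 |
| 3/3χ | 14 + 7 = 21 | 1 × 21 + 14 = 35 | 42 | 63 | 42, 63 | 21 |
| 4/4χ | 21 + 7 = 28 | 0 × 28 + 21 = 21 | 28 | 49 | 28, 49 | 21 |

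With baseline added, this gives 4, 3 and 3 samples, which matches the counts in Protocol Section 10. The ±2-day windows in the cycle schedules turn Cohort 1's 28-day gap into 24 to 32 days. The nominal EOT-to-EOS gap is 28 − 7 = 21 days in every cohort. That is short of 28, and also of 28 − 4 = 24 with the window allowed for.

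Additional cycles improve this. Cohort 4 has a marrow on Day 28 of its first additional cycle, 28 days after the Cycle 1 marrow. Later marrows come every other cycle: with the standard rest, 2 × 14 = 28 days in 14-day cycles and 2 × 21 = 42 days in 21-day cycles.

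**2. When does ORR change?** Table 15 defines MDS SD as no progression for more than 8 weeks (56 days). A short response followed by qualifying SD stays in ORR, and only its category is wrong. A patient leaves ORR only by failing SD as well. Assuming the SD clock starts at first dose (Table 15 does not say), a Cohort 4 patient who stops after the initial cycle has a last scheduled visit at Day 49, which is under 56, so SD cannot be shown. EOS falls at Day 77 in Cohort 1 and Day 63 in Cohort 3, so SD can be shown there if the disease has not progressed.

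**3. What is one patient worth?** About 40 patients are planned and the minimum per cohort is 3; the number with MDS is not given. 1/40 = 2.5 points and 1/3 = 33.3 points. The counts below are assumptions, with exact 95% intervals, for one short response that does not qualify as SD.

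| Patients | All responses counted | One removed |
|---|---|---|
| 5 MDS | 3/5 = 60.0% (14.7–94.7) | 2/5 = 40.0% (5.3–85.3) |
| 10 MDS | 3/10 = 30.0% (6.7–65.2) | 2/10 = 20.0% (2.5–55.6) |
| 15 MDS | 3/15 = 20.0% (4.3–48.1) | 2/15 = 13.3% (1.7–40.5) |
| 40 pooled | 8/40 = 20.0% (9.1–35.6) | 7/40 = 17.5% (7.3–32.8) |

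**The case against.** The SAP imports Section 16.2, heading included, so an investigator could hold back a call until 4 weeks have passed. Protocol Section 14.4 has the investigator review and sign the CRFs once the patient has finished and queries are resolved, so a call could also be corrected. This stands to a point: short responses *can* count, but it is not shown that they will. It does not close the gap. Neither document requires or checks either practice, and the data would not show which convention a site used.

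Table 15 asks that a response last 4 weeks, not that a second marrow prove it. A marrow CR seen at Day 28 and gone by Day 56 may have begun before Day 28. That stands too, and it is why the SAP needs a stated convention for measuring duration.

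A reader might infer that patients leaving Cohorts 3 and 4 after their initial cycles are wrongly counted as responders. The documents do not support that. The 21-day gap exists in Cohort 1 as well, patients who benefit may continue and have further marrows, and a response still present at EOS is of unknown duration, not short.

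The consequence is limited. ORR carries no threshold or test, all response data are listed, and DSMC decisions rest on safety, PD and PK.

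**Conclusion.** The point holds as an omission in the selection rule. As written, SAP Section VIII.A can report an MDS best response that fails the protocol's own definition, on an endpoint tied to a primary objective. The section shows no redaction that could hide a duration rule.

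A reader might go further and infer that MDS response rates and ORR are biased upward by 20 to 33 points. The documents do not support that. Leaving out the duration check can only raise the confirmed-response count or leave it unchanged, but the number of short responses and of MDS patients is unknown, and SD keeps some of these patients in ORR anyway. The supportable size is 2.5 points per patient in a pooled ORR of 40, up to 33 points in a cohort at the minimum of 3, and zero for any patient who qualifies as SD. The timings are nominal: EOT and EOS are approximate, and the detailed follow-up text is not visible.

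**What to change.** Amend SAP Section VIII.A for MDS only:

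1. Define a confirmed CR, PR, marrow CR or cytogenetic response as one still met at an assessment at least 28 days after it was first documented (less the visit window), with no relapse or progression in between. Use marrows from additional cycles where available. Apply the Table 15 footnote on transient cytopenias, and state whether blood counts can support duration between marrows.
2. Show unconfirmed responses in their own row, split into 'lost before 4 weeks' and 'duration not assessable'. A response first seen at EOT and still present at EOS is an example of the second.
3. For ORR, give an unconfirmed response the next category the patient does meet, for example SD if there was no progression for more than 8 weeks. Simply excluding it would rank a brief CR followed by SD below SD alone.
4. Report ORR with and without the not-assessable responses, since treating them all as failures would bias the rate downward.

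The cost is SAP text and programming on data already collected, with no extra procedures. SAP Section I.B allows changes until database lock. The downside is that the confirmed MDS response rate may be lower.
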